2.3 Pharmacokinetic Analysis Set

Not Applicable.

3 Subject Characteristics and Study Conduct Summaries

Subject characteristics and study conduct summaries include tables and listings such as an accountability table (similar to Table A.1 in IS EN ISO 11979-7:2014), demographics (including age, gender, race, ethnicity) and baseline characteristics (including axial length, anterior chamber depth, lens thickness) tables, summary of screen failures by reason, and listing of subjects excluded from analysis sets including reasons. All descriptive summary statistics will be displayed with n and % for categorical data, and with mean, median, standard deviation, number of subjects/eyes, minimum, and maximum for continuous data. Tables will be presented by IOL group and overall.

Subject characteristics and study conduct summaries will be presented for the all-implanted analysis set, the best-case analysis set and the safety analysis set.

4 Effectiveness Analysis Strategy

4.1 Effectiveness Endpoints

Primary and secondary endpoints are listed below. All endpoints are based on assessments at Visit 4A and all visual acuity endpoints are assessed in photopic conditions.

Primary Effectiveness

- Mean monocular best corrected distance visual acuity (4 m) (first operative eye)
- Mean monocular distance corrected visual acuity at near (40 cm) (first operative eye)

Secondary Effectiveness

- Mean monocular distance corrected visual acuity at intermediate (66 cm) (first operative eye)
- Proportion of subjects who respond “Never” to Q1 of the IOLSAT questionnaire.

4.2 Effectiveness Hypotheses

4.2.1 Primary Effectiveness Hypotheses

The null and alternative hypotheses for the first co-primary analysis are:

$$H_0: \mu_{TFNT00_VA} - \mu_{SN60AT_VA} \geq \Delta$$

$$H_A: \mu_{TFNT00_VA} - \mu_{SN60AT_VA} < \Delta$$

Where, Δ refers to the non-inferiority margin, set at 0.10 logMAR, and μ_{TFNT00_VA} and μ_{SN60AT_VA} refer to the population mean monocular best corrected distance visual acuity (4 m) for the test and control lenses, respectively, in the first operative eye at month 6.

The null and alternative hypotheses for the second co-primary analysis are:

$$H_0: \mu_{TFNT00_VA} \geq \mu_{SN60AT_VA}$$

$$H_A: \mu_{TFNT00_VA} < \mu_{SN60AT_VA}$$

Where, μ_{TFNT00_VA} and μ_{SN60AT_VA} refer to the population mean monocular distance corrected visual acuity at near (40 cm) for the test and control lenses, respectively, in the first operative eye at month 6.

4.2.2 Secondary Effectiveness Hypotheses

The null and alternative hypotheses for the first secondary analysis are:

$$H_0: \mu_{TFNT00_VA} \geq \mu_{SN60AT_VA}$$

$$H_A: \mu_{TFNT00_VA} < \mu_{SN60AT_VA}$$

[figure not shown]
Where, μ_{TFNT00_VA} and μ_{SN60AT_VA} refer to the population mean monocular distance corrected visual acuity at intermediate (66 cm) for the test and control lenses, respectively, in the first operative eye at month 6.

The null and alternative hypotheses for the second secondary analysis are:

$$H_0: \pi_{TFNT00_IOLSAT} \leq \pi_{SN60AT_IOLSAT}$$

$$H_A: \pi_{TFNT00_IOLSAT} > \pi_{SN60AT_IOLSAT}$$

Where, π_{TFNT00_IOLSAT} and π_{SN60AT_IOLSAT} , refer to the population proportion of subjects who respond “Never” to Question 1 of the IOLSAT questionnaire at 6 months for the test and control lenses, respectively.

4.3 Statistical Methods for Effectiveness Analyses

A total of four hypothesis tests will be conducted to address the co-primary and secondary objectives of the study. To account for multiplicity, the hypotheses will be tested in sequence, two co-primaries, followed by the first secondary hypothesis, followed by the second secondary hypothesis. The primary effectiveness objective is considered met only if both co-primary hypotheses are met. The type I error for the non-inferiority test is 5% (1-sided) and for the superiority test is 2.5% (1-sided). Each of the secondary hypotheses will be tested at 2.5% (1-sided).

Analysis of the co-primary and first secondary endpoints will begin with a model selection step in an effort to select the most parsimonious model. Two mixed effects models, the first with a fixed effect for treatment and random effect for site, and the second with a fixed effect for treatment and random effects for site and treatment by site interaction, will be fit to the first co-primary endpoint (best corrected distance visual acuity). The two models will be compared using Bayesian information criterion (BIC) and the model with lower BIC will be employed for analysis of all three aforementioned endpoints ^[1, 2].

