Analysis of each co-primary effectiveness endpoint and the first secondary endpoint (at Visit 4A) will be based on a mixed effects model. Two models will be fit to the first co-primary endpoint (BCDVA), 1 with a random effect for site and another with random effects for site and for treatment by site interaction. Both will include a fixed effect for treatment. The 2 models will be compared using Bayesian Information Criterion (BIC) and the model with lower BIC will be the chosen model to estimate the Least Squares Means (LSMEANS) difference in means (AcrySofIQ PanOptix IOL minus AcrySof Monofocal IOL) and the associated confidence intervals for all 3 aforementioned endpoints. The non-inferiority hypothesis will be deemed supported if the upper 95% confidence limit is less than the non-inferiority margin of 0.1 logMAR. Superiority hypotheses will be deemed supported if the upper 97.5% confidence limit is less than 0.0 logMAR.

The second secondary effectiveness endpoint will be analyzed by estimating the Mantel-Haenszel common difference of proportions (AcrySofIQ PanOptix IOL minus AcrySofMonofocal IOL) along with the corresponding confidence interval with site as a stratification variable. Superiority will be declared if the lower 97.5% confidence limit exceeds 0

The co-primary safety objectives are to

- Estimate the cumulative rate of secondary surgical interventions related to the optical properties of the IOL for first operative eyes up to Month 6
- Evaluate the mean binocular contrast sensitivity with and without glare for photopic and mesopic conditions at Month 6.

The secondary safety objective is to

[figure not shown]
- Estimate rates of severe and most bothersome (separately) visual disturbances as reported by the subjects using a questionnaire (QUVID) at Month 6.

The third safety objective is to

- Evaluate rates of cumulative and persistent adverse events in first operative eyes at Month 6 in comparison to the ISO 11979-7 SPE grid rates.

Analysis for the co-primary and secondary safety objectives will involve presenting point estimates (rates or means, depending on type of endpoint) and the corresponding confidence intervals for difference between IOL groups.

Descriptive statistics for adverse events will be

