15.4 Performance Analyses

A total of 4 hypothesis tests will be conducted to address the co-primary and secondary effectiveness objectives of the study. To account for multiplicity, a sequential testing approach consisting of the 2 co-primary hypotheses, followed by the first secondary hypothesis, followed by the second secondary hypothesis will be employed. The primary effectiveness objective is considered met only if both co-primary hypotheses are met. The type I error for the non-inferiority test is 5% (1-sided) and for the superiority test is 2.5% (1-sided). Each of the secondary hypotheses will be tested at 2.5% (1-sided).

Analysis of the co-primary and first secondary endpoints will begin with a model selection step in an effort to select the most parsimonious model. Two mixed effects models, the first with a fixed effect for treatment and random effect for site, and the second with a fixed effect for treatment and random effects for site and treatment by site interaction, will be fit to the first co-primary endpoint (best corrected distance visual acuity). The 2 models will be compared using Bayesian information criterion (BIC) and the model with lower BIC will be employed for analysis of all 3 aforementioned endpoints.

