15.4.1.2 Analysis Methods

Least Squares Means (LSMEANS) from the mixed effects model chosen during the model selection step will be employed to estimate the difference in means (AcrySof IQ PanOptix IOL Model TFNToo minus AcrySof Monofocal IOL Model SN60AT) and the associated confidence intervals for each co-primary endpoint.

The non-inferiority hypothesis (first co-primary) will be deemed supported if the upper 95% confidence limit is less than the non-inferiority margin of 0.10 logMAR.

The superiority hypothesis (second co-primary) will be deemed supported if the upper 97.5% confidence limit is less than 0.0 logMAR.

The above analysis will be repeated for the second eyes [REDACTED]

An analysis with a mixed-effect model analysis of variance (ANOVA) accounting for correlation between the first and the second eye will be performed as a sensitivity analyses.

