4.3.1 Primary Effectiveness Analyses

Least Squares Means (LSMEANS) from the mixed effects model chosen during the model selection step will be employed to estimate the difference in means (AcrySof IQ PanOptix IOL Model TFNT00 minus AcrySof Monofocal IOL Model SN60AT) and the associated 90% (two-sided) confidence interval for the non-inferiority test and 95% (two-sided) confidence interval for the superiority test.

The non-inferiority hypothesis (first co-primary) will be deemed supported if the upper 95% confidence limit is less than the non-inferiority margin of 0.10 logMAR.

The superiority hypothesis (second co-primary) will be deemed supported if the upper 97.5% confidence limit is less than 0.0 logMAR.

SAS pseudo code for the above models is provided below.

```
proc mixed data=visual_acuity;
  where OPERATIVE_EYE = 'First' AND VISIT='VISIT4A';
  class LENS_MODEL SITE;
  model VA = LENS_MODEL /DDFM = satterth;
  random SITE SITE*LENS_MODEL; *[OR] random SITE;
  lsmeans LENS_MODEL / pdiff cl;
  estimate 'Trt_Eff' LENS_MODEL 1 -1;
run;
```

An analysis with a mixed-effect model analysis of variance (ANOVA) accounting for correlation between the first and the second eye will be performed as a sensitivity analyses. The following SAS pseudo code will be used:

```
proc mixed data=visual_acuity;
  where VISIT='VISIT4A';
  class LENS_MODEL SITE OPERATIVE_EYE;
  model VA = LENS_MODEL /DDFM = satterth;
  random SITE SITE*LENS_MODEL; *[OR] random SITE;
  repeated OPERATIVE_EYE / subject=USUBJID(SITE) TYPE=CS;
  lsmeans LENS_MODEL / pdiff cl;
  estimate 'Trt_Eff' LENS_MODEL 1 -1;
run;
```

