Datasets obtained using each of the methods specified above will be analyzed using the model chosen for the primary analysis. The treatment effects and estimates of standard error obtained from each iteration within each method will be combined using PROC MIANALYZE and will be used to draw inferences about each sensitivity analysis. The SAS pseudo code to analyze the imputed datasets and combine the estimates is provided below.

```

/* run mixed model on each iteration of mi */
proc mixed data=mi_out;
  by _imputation_;
  class LENS_MODEL SITE;
  model BCDVA4 = LENS_MODEL /DDFM = satterth;
  random SITE SITE*LENS_MODEL; *[OR] random SITE;
  lsmeans LENS_MODEL / pdiff cl;
  estimate 'Trt_Eff' LENS_MODEL 1 -1;
  ods output Estimates = mimxd_out;
run;

/* generate estimates and CIs from multiple imputation */
proc mianalyze data = mimxd_out ;
  modeleffects estimate;
  stderr stderr;
  ods output ParameterEstimates = Param_out;
run;

```

For the second co-primary safety analysis, a sensitivity analysis imputing some missing data for contrast sensitivity measures is described in the corresponding section (5.3.2).

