4.6 Subgroup Analyses and Effect of Baseline Factors

4.6.1 Subgroup Descriptive Statistics

The consistency of the treatment effect for the co-primary and first secondary endpoints will be assessed descriptively, for both the AAS and BAS, using summary statistics by categories of the following:

- Age category (<65 vs. ≥ 65 years)
- Site
- Ocular Adverse Events (study eyes with vs. study eyes without)
- Preoperative Ocular Pathology (study eyes with vs. study eyes without)

To examine inter-site variation in outcomes, forest plots of co-primary and first secondary endpoints will be produced by plotting the difference in means and corresponding 95% (two-sided) confidence intervals at each site (and by pseudo-site described in Section 2).

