4.6.2 Propensity Score Analysis

A propensity score is the conditional probability of being in the treatment group based on individual covariates at baseline. In a non-randomized study, baseline differences in covariates, amongst groups, may lead to a biased estimate of the treatment effect. To account for these differences the following two-step methodology outlined in (D'Agostino, 1998^[4]) will be employed.

Step 1: Fit a logistic regression model with the following baseline covariates to estimate the probability of being in the treatment group and creating the propensity score weights.

- 1) Age, continuous
- 2) Gender
- 3) Site
- 4) Baseline photopic best-corrected distance visual acuity

The SAS pseudo code for this step is provided below:

```
proc logistic data=Visual_acuity;
  where OPERATIVE_EYE = 'First' AND VISIT='VISIT4A';
  class SEX SITE LENS_MODEL;
  model LENS_MODEL (event='TFNT00') = AGE SEX SITE
    BCDVA_B /link=logit rsquare;
  output out=ps_set pred=ps;
run;

data ps_set;
  set ps_set;
  if TRT='TFNT00' then ps_weight=1/ps;
  else ps_weight=1/(1-ps);
run;
```

Step 2: Fit a propensity score-weighted linear regression model, using the GLM procedure.

```
proc glm data=ps_set;
  where OPERATIVE_EYE = 'First' AND VISIT='VISIT4A';
  class LENS_MODEL;
  model VA = LENS_MODEL /solution;
  weight ps_weight;
  lsmeans LENS_MODEL /pdiff cl;
  estimate 'Trt_eff' LENS_MODEL 1 -1;
run;
```

The estimated treatment effect from the above model will be compared to the estimated effect from the primary analysis mixed effects model. Meaningful differences will be investigated with additional exploratory analyses.

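### Does choosing the random-effects model on distance acuity alone leave the near and intermediate acuity intervals too narrow?

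*SAP*

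**What the plan says.** SAP 4.3 and Protocol 15.4 describe the same selection step. Both models have a fixed lens effect. One has a random site effect and the other adds a random lens-by-site effect. Both models "will be fit to the first co-primary endpoint (best corrected distance visual acuity"), and then "the model with lower BIC will be employed for analysis of all three aforementioned endpoints". The three endpoints are BCDVA (non-inferiority), DCNVA (superiority, co-primary) and DCIVA (superiority, first secondary). The Protocol synopsis agrees: "The 2 models will be compared using Bayesian Information Criterion (BIC) and the model with lower BIC will be the chosen model".

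The code in SAP 4.3.1 prints both options on one line, "random SITE SITE*LENS_MODEL; *[OR] random SITE", and SAP 4.3.2.1 uses the same code for DCIVA. Other visible analyses that bear on the point:

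- Imputation analyses (SAP 4.5, co-primaries only): "Datasets obtained using each of the methods specified above will be analyzed using the model chosen for the primary analysis".
- Second eyes (Protocol 15.4.1.2): "The above analysis will be repeated for the second eyes". Protocol 15.4.2.2 has a similar sentence for DCIVA.
- Two-eye sensitivity analysis (SAP 4.3.1): code with the same either/or line.
- Propensity analysis (SAP 4.6.2): "Fit a propensity score-weighted linear regression model, using the GLM procedure". Site enters the propensity model, but the outcome model contains lens only.
- Site display (SAP 4.6.1): "To examine inter-site variation in outcomes, forest plots of co-primary and first secondary endpoints will be produced".

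**The concern.** BCDVA is the endpoint on which the lenses are assumed equal. DCNVA and DCIVA are those on which a 0.1 logMAR difference is assumed. Nothing in the documents says that site-to-site variation in the lens effect is shared across distances, and in a non-randomized study with lens choice made at the site such variation is plausible. BCDVA could therefore point to the site-only model while the near or intermediate effect varies by site. The intervals behind one co-primary and the first secondary claim would then leave out a source of variance. No other visible analysis is clearly told to fit the lens-by-site term whichever model BIC picks. At stake would be the 2.5% one-sided error rate for two superiority claims.

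**Working it through.** **Inputs.** From SAP 7: SD 0.18, difference 0.1, margin 0.1, 113 completers per arm. From Protocol 10: about 12 sites, about 10 subjects per arm per site. The lens-by-site component SD, called s, is not given and is assumed at 0 / 0.03 / 0.05 / 0.07 logMAR. The SD of the lens difference between sites is s√2 = 0 / 0.042 / 0.071 / 0.099, so the last value is about the whole planned effect.

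**1. The plan's own power.** SE = √(2 × 0.18² / 113) = 0.0239, and 0.1 / 0.0239 = 4.18.
- Superiority: Φ(4.18 − 1.96) = 98.7% (stated 98%).
- Non-inferiority: Φ(4.18 − 1.645) = 99.4% (stated 99%).

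Both figures reproduce. Neither includes a lens-by-site variance.

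**2. What omitting the term could do.** With the term, SE = √(2 × 0.18² / 113 + 2s² / 12). At s = 0.05 this is √(0.000573 + 0.000417) = 0.0315, or 1.314 times the site-only SE. A nominal 2.5% one-sided test would then run at about Φ(−1.96 / 1.314) = 6.8%.

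**3. The whole rule, simulated.** Setup: 12 sites × 2 lenses × 9 per cell (108 per arm, near the required 113), residual SD 0.18, site SD 0.05 (assumed), REML, BIC penalty log(12), 200,000 runs, true difference 0.10 for coverage and power.

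| s for DCNVA | 0 | 0.03 | 0.05 | 0.07 |
|---|---|---|---|---|
| 95% coverage, BCDVA has no such variation | 95.1 | 92.3 | 87.9 | 82.0 |
| 95% coverage, BCDVA has the same amount | 95.1 | 92.6 | 90.2 | 89.9 |
| 95% coverage, BIC run on DCNVA itself | 95.2 | 93.2 | 91.3 | 91.5 |
| 95% coverage, term always fitted | 96.5 | 95.6 | 95.1 | 94.6 |
| One-sided error, no BCDVA variation | 2.5 | 3.8 | 6.0 | 9.1 |
| One-sided error, same amount | 2.5 | 3.7 | 4.9 | 5.1 |

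Unequal cells (4 to 14 per cell) and site SDs of 0.02 or 0.10 gave similar coverage. Pooling into a pseudo-site was not simulated.

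**4. Where the shortfall comes from.** When BCDVA varies by the same amount, the shortfall from 95% at s = 0.03 / 0.05 / 0.07 is 2.3 / 4.9 / 5.0 points. Selecting on BCDVA instead of on DCNVA accounts for only about 0.5 / 1.1 / 1.5 of those points. The rest is BIC's low sensitivity with 12 sites: it picks the larger model in just 13 / 35 / 64% of runs. Selecting separately on each endpoint would leave most of the problem in place.

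**5. Coverage of what.** The losses in step 3 are measured against a hypothetical population of sites. For the average lens difference over the sites actually enrolled, the site-only interval (100,000 runs, same layout) covers 95.0 / 95.2 / 95.3 / 95.8%. The hypotheses in SAP 4.2 speak only of population means and do not settle which target is meant.

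**6. What the alternatives buy.** Power at a 0.10 difference:

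| s | 0 | 0.03 | 0.05 | 0.07 |
|---|---|---|---|---|
| Rule, no BCDVA variation | 98.1 | 96.7 | 93.9 | 89.9 |
| Rule, same amount | 98.2 | 96.3 | 90.5 | 77.7 |
| Term always fitted | 96.1 | 92.0 | 83.1 | 70.5 |

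In the balanced layout both models give the same estimate and the larger model's interval is at least as wide. The difference in power is therefore the share of runs in which the two intervals disagree about zero: about 2 / 5 / 11 / 19% with no BCDVA variation, and 2 / 4 / 7 / 7% with the same amount. The 2% at s = 0 arises with no true variation at all.

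**7. The two-eye code.** The SAP says the printed code will be used for this sensitivity analysis. It does not tie that analysis to the selected model, as the primary text does. In SAS a statement that starts with an asterisk is a comment, so the code as printed fits SITE*LENS_MODEL. The text is ambiguous, but it cannot be read as clearly leaving the term out.

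**The case for a change.** The strongest case for a change is that one SAP sentence could ask for the larger model as a sensitivity analysis for DCNVA and DCIVA whichever model BIC picks. It would need no new data and no protocol amendment, it would leave alpha and power alone, and it would avoid a post-hoc choice if the forest plots show marked site differences. The random site term also makes a wider population of sites an arguable target, and the natural reading of the two-eye code is that it follows the primary choice.

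Much of this stands. The rule does carry a choice across endpoints, the simulated losses are real under their assumptions, and the forest plots are descriptive and alter no interval. What does not follow is that the plan must change. The added interval would decide nothing, and the plots already show each site's difference with its 95% interval for all three acuity endpoints. The largest losses need DCNVA to vary by site while BCDVA varies not at all, and the documents give no support for that pairing. Parts of both documents near these sections are redacted, so a claim that no such analysis exists can cover the visible text only.

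**Conclusion.** No change is needed. A single structure, fixed in advance on the first co-primary and stated alike in the Protocol and SAP, is a fair trade-off. It avoids a separate data-driven choice for each endpoint and keeps power near the planned figure if lens-by-site variation is small.

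The possible cost depends on an unstated variance. With none, nothing is lost. With an assumed component SD of 0.03 to 0.07 logMAR and a wider population of sites as the target, DCNVA coverage falls to about 92% to 82% (no BCDVA variation) or about 93% to 90% (same amount). For the average over enrolled sites there is no shortfall. DCIVA follows the same reasoning, since it has the same assumed SD, difference and code.

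The change that would alter the deciding interval is to make the larger model primary. That would lower power to about 83% at an SD of 0.05 and contradict the Protocol's rule, with 250 subjects already enrolled when this SAP version was written. Marked site variation would be visible in the forest plots, and the analyst can report the larger model as supplementary without amending the plan. These figures assume 12 sites with about 9 subjects per cell.

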4.3.1 Primary Effectiveness Analyses

Least Squares Means (LSMEANS) from the mixed effects model chosen during the model selection step will be employed to estimate the difference in means (AcrySof IQ PanOptix IOL Model TFNT00 minus AcrySof Monofocal IOL Model SN60AT) and the associated 90% (two-sided) confidence interval for the non-inferiority test and 95% (two-sided) confidence interval for the superiority test.

The non-inferiority hypothesis (first co-primary) will be deemed supported if the upper 95% confidence limit is less than the non-inferiority margin of 0.10 logMAR.

The superiority hypothesis (second co-primary) will be deemed supported if the upper 97.5% confidence limit is less than 0.0 logMAR.

SAS pseudo code for the above models is provided below.

```
proc mixed data=visual_acuity;
  where OPERATIVE_EYE = 'First' AND VISIT='VISIT4A';
  class LENS_MODEL SITE;
  model VA = LENS_MODEL /DDFM = satterth;
  random SITE SITE*LENS_MODEL; *[OR] random SITE;
  lsmeans LENS_MODEL / pdiff cl;
  estimate 'Trt_Eff' LENS_MODEL 1 -1;
run;
```

An analysis with a mixed-effect model analysis of variance (ANOVA) accounting for correlation between the first and the second eye will be performed as a sensitivity analyses. The following SAS pseudo code will be used:

```
proc mixed data=visual_acuity;
  where VISIT='VISIT4A';
  class LENS_MODEL SITE OPERATIVE_EYE;
  model VA = LENS_MODEL /DDFM = satterth;
  random SITE SITE*LENS_MODEL; *[OR] random SITE;
  repeated OPERATIVE_EYE / subject=USUBJID(SITE) TYPE=CS;
  lsmeans LENS_MODEL / pdiff cl;
  estimate 'Trt_Eff' LENS_MODEL 1 -1;
run;
```

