4.5 Handling of Missing Data

The AAS and BAS do not include any imputed values for the co-primary effectiveness endpoints, best corrected distance visual acuity and distance corrected near visual acuity. Although the influence of missing data is expected to be minimal, the following sensitivity analyses will be conducted to assess the impact of missing data on the conclusions from the co-primary effectiveness analyses.

1. Multiple imputation (with a fully conditional specification) method will be used to impute and estimate the treatment effect.

2. The sensitivity of inferences to departures from the missing-at-random (MAR) assumption will be examined using a pattern-mixture model approach (with a control-based pattern imputation^[3]).

Sensitivity Analysis 1:

A fully conditional specification (FCS) method will be used to impute missing monocular best corrected distance visual acuity at 4 m (first operative eye) values and monocular distance corrected visual acuity at near (first operative eye) at month 1 and month 6 visits in a data set with an arbitrary missing pattern. The FCS method uses a separate conditional distribution for each imputed variable.

The following SAS pseudo-code with the PROC MI procedure will be used to impute missing BCDVA values (or DCNVA) using FCS method:

```
/* multiple imputation w/ MAR assumption          */
/* BCDVA3-BCDVA4 should be in wide format      */
proc mi data=mi_in seed=1561 n impute=100 mu0=.1 .0 out=mi_out;
  fcs nbiter=100 reg; *reg(/details);
  var BCDVA3 BCDVA4;
run;
```

Sensitivity Analysis 2:

The sensitivity of inferences to departures from the MAR assumption will be examined using a pattern-mixture model approach with a control-based pattern imputation.

The following SAS pseudo-code with the PROC MI procedure will be used to implement the control-based pattern imputation:

```
/* multiple imputation w/ MNAR assumption          */
/* BCDVA3-BCDVA4 should be in wide format      */
proc mi data=mi_in seed=1561 n impute=100 mu0=.1 .0 out=mi_out;
  class LENS_MODEL;
  fcs nbiter=100 reg; *reg(/details);
  mnar model(BCDVA3 BCDVA4 / modelobs=(LENS_MODEL='SN60AT'));
  var BCDVA3 BCDVA4;
run;
```

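### The SAP's SAS pseudo code returns SN60AT minus TFNT00 under default level ordering, opposite to its own text and decision rules, and omits the 90% level for the distance-vision interval: a minor code-to-text correction before lock

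*SAP*

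**What the plan says.** SAP 4.3.1 sets the direction in words: the difference is "AcrySof IQ PanOptix IOL Model TFNT00 minus AcrySof Monofocal IOL Model SN60AT", estimated by least squares means from the chosen mixed model. Non-inferiority in best corrected distance acuity (BCDVA) requires the upper 95% limit to lie below 0.10 logMAR. Superiority in distance corrected near acuity (DCNVA) requires the upper 97.5% limit to lie below 0. The same section asks for a 90% two-sided "confidence interval for the non-inferiority test and 95% (two-sided) confidence interval for the superiority test". SAP 4.3.2.1 applies the superiority rule to distance corrected intermediate acuity (DCIVA) and says its code is identical to the primary code. The SAP hypotheses in 4.2 run in the same direction.

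The PROC MIXED block in 4.3.1 contains "class LENS_MODEL SITE" with no ordering option, then "lsmeans LENS_MODEL / pdiff cl" and "estimate 'Trt_Eff' LENS_MODEL 1 -1". The two-eye sensitivity model in 4.3.1 and the imputation model in 4.5 use the same contrast. In 4.5 the contrast is saved by "ods output Estimates = mimxd_out" and passed to PROC MIANALYZE. The propensity-weighted PROC GLM step in 4.6.2 has "estimate 'Trt_eff' LENS_MODEL 1 -1".

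The SAP's own code supplies the level values. The control is named in 4.5 by "modelobs=(LENS_MODEL='SN60AT", and the event level in the logistic model of 4.6.2 is TFNT00.

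**The concern.** SAS orders the levels of a CLASS variable by ascending formatted value unless told otherwise. SN60AT sorts before TFNT00, so coefficients 1 and -1 give control minus test. The LSMEANS difference takes the first level minus the second, so it has the same direction. That line matters more, because the ESTIMATE statement carries no CL option and prints no confidence limits.

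The decision rules, however, are written for test minus control. Lower logMAR means better vision, so a reversed sign is easy to misread. A programmer who follows the block and compares the printed upper limit with 0.10 or 0 tests the mirror image of each hypothesis, for both co-primaries and the first secondary.

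Separately, with no ALPHA= option SAS prints 95% two-sided limits, so the 90% interval specified for BCDVA is not produced. PROC MIANALYZE has no level stated either.

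**Working it through.** **Inputs.** From SAP section 7: 113 completers per arm, common SD 0.18 logMAR, planned difference 0 for BCDVA and 0.1 in favour of the test lens for DCNVA and DCIVA. From SAP 4.3 and 4.3.1: margin 0.10; one-sided 5% for non-inferiority and 2.5% for superiority.

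**Level order.** Sorting the two values gives SN60AT, then TFNT00. This rests on the SAS default, which the SAP neither states nor overrides.

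**Standard error.** SE = 0.18 × √(2/113) = 0.02395. Site random effects are left out; they do not affect the sign.

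**The plan's own power.** The normal approximation is Φ(0.10/SE − z), with 0.10/0.02395 = 4.176.
- Non-inferiority: Φ(4.176 − 1.645) = 99.4% (noncentral t, 224 df: 99.4%). The plan states 99%.
- Superiority: Φ(4.176 − 1.960) = 98.7% (noncentral t: 98.6%). The plan states 98%.

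Both figures are reproduced.

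**Effect of direction.** Let D be the true TFNT00 − SN60AT difference. In the direction of the text, P(pass) = Φ((threshold − D)/SE − z). For the printed contrast, replace D by −D.
- Non-inferiority at D = +0.10: text Φ(0 − 1.645) = 5.0%; code Φ(8.352 − 1.645) = Φ(6.707), above 99.99%.
- Superiority at D = −0.10: text 98.7%; code Φ(−4.176 − 1.960) = Φ(−6.136), about 4 × 10⁻¹⁰.

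| True TFNT00 − SN60AT | Test | Direction in text | Direction in code |
|---|---|---|---|
| +0.10 | Non-inferiority | 5.0% | >99.99% |
| 0 | Non-inferiority | 99.4% | 99.4% |
| −0.10 | Non-inferiority | >99.99% | 5.0% |
| −0.10 | Superiority | 98.7% | 4 × 10⁻¹⁰ |
| +0.10 | Superiority | 4 × 10⁻¹⁰ | 98.7% |

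A 20,000-run two-sample simulation agreed: at D = +0.10 non-inferiority passed in 5.1% (text) and 100% (code) of runs; at D = −0.10 superiority passed in 98.7% and 0%.

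**One observed result.** If DCNVA comes out at −0.10, the upper 97.5% limit is −0.10 + 1.960 × 0.02395 = −0.053 and superiority is met. Reversed, it is +0.10 + 0.047 = +0.147 and superiority fails.

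**Both co-primaries together.** Under the plan's assumptions (BCDVA difference 0, DCNVA difference −0.10), the reversed output passes both only if it passes superiority. The chance of declaring overall success is therefore at most about 4 × 10⁻¹⁰.

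**Missing interval level.** Using the upper limit of a 95% two-sided interval for BCDVA amounts to a one-sided 2.5% test. By noncentral t, power at a true difference of 0 falls from 99.4% to 98.6%, which is 0.8 percentage points in the conservative direction.

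**The case against.** The strongest reply is that the governing specification is right. The direction is stated in words in SAP 4.3.1 and 4.3.2.1 and in Protocol 15.4.1.2 and 15.4.2.2, and it agrees with the SAP hypotheses and every decision rule. The blocks are labelled pseudo code and plainly are not a finished program: alternative RANDOM statements sit side by side, the propensity step models one treatment variable and then branches on another, and 4.5 shows BCDVA only. SAS also labels each LSMEANS difference with both lens models and prints both group means, so an unnoticed reversal would require the analyst to overlook several cues. All of this stands, and it keeps the point small.

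Two stronger readings are tempting. A reader might infer that the trial's decision rule is wrong. The documents do not support that, since only the code departs from the rule. A reader might also infer that a lens with inferior distance vision would be carried to overall success. SAP 4.4 requires both co-primaries to be met, so a lens worse at distance but better at near would fail the reversed superiority test. A false overall success would need a trifocal that is worse than the monofocal at near.

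The propensity comparison in 4.6.2 also survives as a comparison, because both of its estimates carry the same reversed sign.

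What the reply does not remove is that the code printed for three confirmatory tests and the missing-data analyses contradicts the text, and nothing tells the programmer to change the sign. At a true BCDVA difference of 0, both directions give 99.4%, so the planning figure for that endpoint would not expose the reversal.

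**Conclusion.** The point holds as a minor inconsistency between code and text. Under default level ordering, the pseudo code in SAP 4.3.1, 4.5 and 4.6.2, and by reference 4.3.2.1, estimates the reverse of the defined difference. It also omits the level for the 90% BCDVA interval, a small conservative discrepancy.

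If the output went into the rules unchanged, each individual test would be reversed. The likely visible consequence is a false failure of superiority at near. The figures assume 113 per arm, SD 0.18 and no site effect. The direction assumes SAS's default ordering of the two level values; a production program with a different order would remove the sign problem.

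It is still worth correcting before lock. Otherwise the sign of the primary result may have to be changed with outcomes in view, in a non-randomized study where subjects and investigators know the lens.

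One separate matter: in the copy reviewed, the non-inferiority inequalities in Protocol 15.4.1.1 read opposite to those in SAP 4.2.1. The symbols there are damaged by text extraction, so nothing here depends on them, but the original should be checked.

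**What to change.** Before database lock:

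- **SAP 4.3.1, and 4.3.2.1 by reference.** State the direction in the line that supplies the limits: `lsmeans LENS_MODEL / pdiff=control('SN60AT') cl alpha=0.10` for BCDVA, and the same with `alpha=0.05` for DCNVA and DCIVA.
- **ESTIMATE contrasts in 4.3.1 (both models), 4.5 and 4.6.2.** Make each one TFNT00 minus SN60AT and state the level order explicitly. Changing the coefficients to -1 and 1 without doing so would still depend on an unstated default, and would leave the LSMEANS line reversed.
- **SAP 4.5.** Give PROC MIANALYZE `alpha=0.10` for BCDVA.
- **SAP 4.6.2.** Correct only the contrast and the LSMEANS direction. ESTIMATE in PROC GLM does not accept CL or ALPHA= options; if limits on that line are wanted, add CLPARM to the MODEL statement.

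The cost is a few lines of SAP code. No hypothesis, margin, sample size or data collection changes.
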